5.1.3 Subject Exclusion Criteria

The subject must be excluded from participating in the trial if the subject:

1. has received any amount of effective antibiotic therapy (defined as therapy known to be active against the identified pathogen) after obtaining the culture for admission to this study (admission culture) and prior to the administration of the first dose of IV study therapy.

Note: For subjects with cIAI, use of intra-operative antibiotics per each institution's standard procedure is allowed.

2. has received treatment with systemic effective antibiotics for > 24 hours within the 72 hours immediately prior to initiation of study therapy.

NOTE: For a subject has received >48 hours of systemic antimicrobial therapy, he/she is eligible for this study if there are clear evidence that the subject has failed this regimen or developed the current index infection while on the previous antibiotic regimen. Such evidence would include new or continued fever or persistence or worsening of symptoms related to the index infection and persistent laboratory or radiographic changes (if previously present). In addition, investigators should confirm the evidence of positive cultures which suggests persistent bacterial infection. Culture results do not need to be known before entry; however, the evidence should be obtained as support the presence of bacteria in sample from index infection such as Gram stain. These measures should be confirmed prior to study entry.

3. has a concurrent infection that would interfere with evaluation of response to IMI/REL, including any of the following:

- endocarditis
- osteomyelitis
- meningitis
- prosthetic joint infection

4. has a cIAI or cUTI due to a confirmed fungal pathogen.

NOTE: Use of antifungal therapy for treatment of mucocutaneous infections (e.g., vaginal candidiasis or onychomycosis) is allowed (see Section 5.5).

5. has cUTI which meets any of the following:

- complete obstruction of any portion of the urinary tract (requiring a permanent indwelling urinary catheter or instrumentation)
- known ileal loop
- intractable vesico-uretral reflux
- presence of indwelling urinary catheter which cannot be removed at study entry

NOTE: All indwelling urinary catheters must be removed prior to the start of IV therapy. Unless medically necessary, it is recommended that an indwelling urinary catheter not be reinserted while on IV study therapy.

6. has cIAI which meets any of the following:

- Subject has an infection which should be managed by Staged Abdominal Repair (STAR) or open abdomen technique.
- Infections limited to the hollow viscus, such as simple cholecystitis and simple appendicitis, ischemic bowel disease without perforation, acute suppurative cholangitis and acute necrotizing pancreatitis

7. has a history of serious allergy, hypersensitivity (e.g., anaphylaxis), or any serious reaction to any of the following:

- Any carbapenem, cephalosporin, penicillin, or other β -lactam agent
- other β -lactamase inhibitors (e.g., tazobactam, sulbactam, clavulanic acid, avibactam)

8. is a female who is pregnant or is expecting to conceive (or is a male partner of a female who is expecting to conceive), is breastfeeding, or plans to breastfeed prior to completion of the study.

9. has a history of a seizure disorder (requiring ongoing treatment with anti-convulsive therapy or prior treatment with anti-convulsive therapy within the last 3 years).

10. is anticipated to be treated with any of the following medications during the course of study therapy:

- valproic acid (or has used valproic acid in the 2 weeks prior to screening)
- concomitant IV or oral antimicrobial treatments which is considered effective to the index pathogen, in addition to the study treatments.

NOTE: Use of IV vancomycin, IV daptomycin, or IV linezolid to treat confirmed or suspected methicillin-resistant *S. aureus* (MRSA) infection or use of IV linezolid to treat confirmed or suspected vancomycin-resistant *Enterococcus spp.* (VRE) infection is allowed. (Refer to Section 5.5).

11. is currently receiving immunosuppressive therapy, including use of high-dose corticosteroids (i.e., \geq 40 mg prednisone or prednisone equivalent per day).

NOTE: Prior short term use (\leq 7 days) of steroid therapy in the 30 days prior to study entry is allowed.

12. has an estimated or actual creatinine clearance of less than 15 mL/min at screening based on the findings of local laboratory values. Creatinine clearance in mL/min may be calculated from serum creatinine concentration by the C-G equation:

$$\text{Creatinine clearance (Males)} = \frac{\text{weight in kg} \times (140 \text{ minus age})}{(72) \times (\text{creatinine in mg/dL})}$$

Creatinine clearance (Females) = 0.85 \times the value obtained using the formula above

13. is currently undergoing hemodialysis or peritoneal dialysis.

14. has any of the following laboratory abnormalities at the time of screening:

- Alanine aminotransferase (ALT) values \geq 4 times the upper limit of normal (ULN)
- Aspartate aminotransferase (AST) values \geq 4 times ULN
- ALT or AST $\geq 3 \times$ ULN and total bilirubin $\geq 2 \times$ ULN and, at the same time, Alkaline phosphatase (ALP) $< 2 \times$ ULN
- Total bilirubin value \geq 3 times ULN

NOTE: Subjects with acute hepatic failure or acute decompensation of chronic hepatic failure should also be excluded.

15. has a history or current evidence of any condition, therapy, laboratory abnormality, or other circumstance that, in the opinion of the investigator, might confound the results of the study, interfere with the subject's participation for the full duration of the study, or pose additional risk in administering the study drugs to the subject.

16. is currently participating in, or has participated in, any other clinical study involving the administration of investigational or experimental medication (not licensed by regulatory agencies) at the time of the presentation or during the previous 30 days prior to screening or is anticipated to participate in such a clinical study during the course of this trial.
17. has previously participated in this study at any time
18. Is or has an immediate family member (e.g., spouse, parent/legal guardian, sibling or child) who is investigational site or Sponsor staff directly involved with this trial.

5.2 Trial Treatment(s)

The treatment(s) to be used in this trial is outlined below in [Table 12](#).

Table 12 Trial Treatment

Drug	Dose/Potency	Dose Frequency	Route of Administration	Treatment Period	Use
Imipenem/cilastatin/ relebactam (IMI/REL)	Imipenem: 500 mg Relebactam:250 mg	Every 6 hours	IV	5 to 14 days	experimental

The first dose of prescribed study therapy should be administered at the Day 1 visit. Subjects will receive a minimum of 5 days to up to a maximum of 14 days of intravenous (IV) study therapy.

Detailed dosing guidelines, including dose selection and timing of dose administration, are outlined in Section 5.2.1 and Section 5.2.2, respectively.

The investigator shall take responsibility for and shall take all steps to maintain appropriate records and ensure appropriate supply, storage, handling, distribution and usage of trial treatments in accordance with the protocol and any applicable laws and regulations.

5.2.1 Dose Selection/Modification

5.2.1.1 Dose Selection (Preparation)

The chosen dose for IMI/REL in subjects with normal renal function is IMI/REL 500mg/250 mg administered IV as an FDC once every 6 hours (q6h). For subjects with renal insufficiency or whose creatinine clearance changes during treatment with study therapy, the dose must be adjusted based upon the degree of renal function impairment, as determined by the estimated or actual creatinine clearance. Subjects should be carefully monitored for renal function during IV treatment. Dose adjustments are included in [Table 13](#).

Table 13 Administration Dosage of IMI/REL According to Renal Function

Creatinine Clearance (mL/min)	IMI/REL ^a
≥ 90	500/250 mg q6h
< 90 to ≥ 60	400/200 mg q6h
< 60 to ≥ 30	300/150 mg q6h
< 30 to ≥ 15	200/100 mg q6h

^a IMI/REL is provided as a single vial in a fixed-dose combination; therefore, the dose for each component will be adjusted equally during preparation. For example, a subject who has a creatinine clearance of 50 mL/min should receive a 300/150 mg q6h dose of IMI/REL according to the table.

Creatinine clearance in mL/min may be calculated from serum creatinine concentration by the following equation:

$$\text{Creatinine clearance: (Males)} = \frac{(\text{weight in kg}) \times (140 \text{ minus age})}{(72) \times (\text{creatinine in mg/dL})}$$

Creatinine clearance: (Females) = 0.85 X the value obtained using the formula above.

5.2.2 Timing of Dose Administration

As shown in [Table 13](#), the dose of IMI/REL may need to be adjusted based on the subject's renal function. The frequency of administration will not change. Each infusion should be administered within 60 minutes of the scheduled dose.

IMI/REL should be administered over 30 minutes +/- 5 minutes. The study therapy must NOT be administered simultaneously through the same infusion line/lumen with any other drugs (including IV non-study drugs). If another IV drug is required either prior to or after study drug and only 1 line/lumen is available, an appropriate volume of saline flush must be used between IV infusions.

Additional details for preparation and administration of study drug are provided in a separate Pharmacy Manual.

5.2.3 Trial Blinding

This is an open-label trial; therefore, the Sponsor, investigator and subject will know the treatment administered.

5.3 Randomization or Treatment Allocation

Subjects participating in this trial will be allocated by non-random assignment using an integrated web response system (IWRS).

5.4 Stratification

No stratification based on age, sex or other characteristics will be used in this trial.

5.5 Concomitant Medications/Vaccinations (Allowed & Prohibited)

Medications or vaccinations specifically prohibited in the exclusion criteria are not allowed during the ongoing trial. If there is a clinical indication for any medication or vaccination specifically prohibited during the trial, discontinuation from trial therapy or vaccination may be required. The investigator should discuss any questions regarding this with the Sponsor Clinical Director. The final decision on any supportive therapy or vaccination rests with the investigator and/or the subject's primary physician. However, the decision to continue the subject on trial therapy or vaccination schedule requires the mutual agreement of the investigator, the Sponsor and the subject.

The following concomitant medications/therapies are not permitted in this study:

1. Valproic acid (during treatment with study drug and the 2 weeks prior to screening)
2. Non-study systemic (IV or oral) antibacterial treatments

NOTE: Use of IV vancomycin, IV daptomycin, or IV linezolid to treat confirmed or suspected methicillin-resistant *S. aureus* (MRSA) infection or use of IV linezolid to treat confirmed or suspected vancomycin-resistant *Enterococcus* spp. (VRE) infection is allowed.

3. Systemic (IV or oral) antifungal therapy

NOTE: Concomitant use of antifungal therapy for treatment of mucocutaneous infections (e.g., vaginal candidiasis, onychomycosis) is allowed.

4. Immunosuppressive therapy, including use of high-dose corticosteroids (i.e., ≥ 40 mg prednisone or prednisone equivalent per day)

NOTE: Short-term use (≤ 7 days) of systemic (Oral or IV) steroid therapy and Topical steroids for the treatment of skin conditions are also allowed.

5.6 Rescue Medications & Supportive Care

No rescue or supportive medications are specified to be used in this trial.

5.7 Diet/Activity/Other Considerations

There are no dietary or activity restrictions in this study, except as medically indicated.

5.8 Subject Withdrawal/Discontinuation Criteria

5.8.1 Discontinuation of Treatment

Discontinuation of treatment does not represent withdrawal from the trial.

As certain data on clinical events beyond treatment discontinuation are important to the study, they must be collected through the subject's last scheduled follow-up, even if the subject has discontinued treatment. Therefore, all subjects who discontinue trial treatment prior to completion of the treatment period will still continue to participate in the trial as specified in Section 6.0 - Trial Flow Chart and Section 7.1.5.3 – Discontinued Subjects Continuing to be Monitored in the Trial.

Subjects may discontinue treatment at any time for any reason or be dropped from treatment at the discretion of the investigator should any untoward effect occur. In addition, a subject may be discontinued from treatment by the investigator or the Sponsor if treatment is inappropriate, the trial plan is violated, or for administrative and/or other safety reasons. Specific details regarding procedures to be performed at treatment discontinuation are provided in Section 7.1.4 – Other Procedures.

A subject must be discontinued from treatment but continue to be monitored in the trial for any of the following reasons:

- The subject or subject's legally acceptable representative requests to discontinue treatment.
- Any of the following post-baseline elevations in liver transaminase levels:

In subjects without baseline transaminase elevations:

- ALT or AST ≥ 8 X ULN
- ALT or AST ≥ 3 X ULN accompanied by total bilirubin > 2 X ULN or INR > 1.5
- ALT or AST ≥ 3 X ULN with the appearance of fatigue, nausea, vomiting, right upper quadrant pain or tenderness, fever (defined as oral temperature $\geq 38.0^{\circ}\text{C}$), rash, and/or eosinophilia ($> 5\%$)

NOTE: In subjects in whom fatigue, nausea, vomiting, and right upper quadrant pain or tenderness was a part of the subject's presenting illness, the subject may continue on therapy if there is no elevation in transaminases from baseline measurements. In such subjects who experience a return of their original symptoms with accompanying elevations in transaminases it may be difficult to determine the cause, and investigators may discuss subjects in this situation with the Sponsor Clinical Director prior to discontinuation, if desired.

In subjects with preexisting transaminase elevations,

- Further increase in transaminases to ≥ 8 X ULN that is not anticipated from their underlying medical condition.
- ALT or AST ≥ 3 X ULN [with at least 50% increase from transaminase values collected at Day 1] and new onset of clinical signs and symptoms of fatigue, nausea, vomiting, right upper quadrant pain or tenderness, fever (defined as oral temperature $\geq 38.0^{\circ}\text{C}$), rash, and/or eosinophilia ($> 5\%$)
- Clinically significant worsening of liver function associated with further transaminase elevations in a subject with abnormal transaminase levels already meeting the above criteria (i.e., ≥ 8 X ULN; ALT or AST ≥ 3 X ULN [with at least 50% increase from transaminase values collected at Day 1] and new onset of clinical signs and symptoms listed) at baseline.

The subject will discontinue from study therapy, but will continue to participate in the study and will be assessed according to all study planned study procedures through the final study visit and will be evaluated for blood chemistry and hematology (including, at minimum, ALT, AST, alkaline phosphatase, bilirubin (direct + indirect) and creatine phosphokinase) until values return to within normal range. The trial site guidance for assessment and follow up of liver function test (LFT) elevations can be found in the Investigator Trial File Binder.

- A post-baseline decline in estimated or actual creatinine clearance to a value of less than 15 mL/min.
- The subject requires initiation of hemodialysis or peritoneal dialysis.
- The subject has a confirmed positive serum or urine (sensitivity of < 25 million IU/L is required if using urine test) pregnancy test.
- A physician investigator feels it is in best interest of the subject to discontinue for any reason, including, but not limited to, the need for alternative non-study antibacterial therapy.

For subjects who are discontinued from treatment but continue to be monitored in the trial, all visits and procedures, as outlined in the trial flowchart, should be completed.

Discontinuation from treatment is “permanent.” Once a subject is discontinued, he/she shall not be allowed to restart treatment.

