8.5.2 Efficacy Analysis Population

Two populations, the MITT and the ME populations, will be used for the analysis of efficacy data in this study. The ME population will serve as the primary population for efficacy analyses in this study.

The MITT population is defined as all enrolled subjects who receive at least one dose of IV study therapy. In this study, this is identical with the ASaT population. The ME population is a subset of the MITT population that excludes subjects due to major deviations from the protocol that may substantially affect the results of the efficacy analyses. Potential deviations that may result in the exclusion of a subject from the ME population include the following:

1. The subject fails to meet the protocol definition of cIAI or cUTI
2. The subject had significant violations of inclusion/exclusion criteria that could impact the efficacy assessment (e.g., receipt of previous or concurrent systemic antibacterial therapy beyond those allowed per protocol)
3. The subject received less than 96 hours of IV study therapy (16 infusions)
4. (cIAI only) The subject's pre-study/post-operative culture from the site of infection fails to grow at least 1 gram-negative enteric(s) and/or anaerobic pathogen(s) commonly isolated in IAI. (Note: Subjects who fail to grow a single gram-negative enteric and/or anaerobic pathogen from the site of infection are excluded from the ME population. That is, subjects with only gram-positive pathogens identified will be excluded, as well as those who do not grow any pathogens.)

(cUTI only) The subject's pre-study urine culture fails to grow at least 1 gram-negative and/or anaerobic, pathogen at sufficient quantity specified in the inclusion criteria (See Section 5.1.2 for details)

The composition of the ME population at each time point of interest will be made prior to the database lock and will be documented in a separate memo.

Details on the approach to handling missing data are provided in Section 8.6.

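### The worsening-liver-function stop for subjects with preexisting transaminase elevations (5.8.1) is practically empty, and no bilirubin or INR stop fills the gap

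*Combined protocol and SAP*

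**What the plan says.** Section 5.8.1 requires treatment to stop for "Any of the following post-baseline elevations in liver transaminase levels", in two branches.

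- **No baseline elevation.** Stop at ALT or AST of 8 X ULN or more; at 3 X ULN or more "accompanied by total bilirubin > 2 X ULN or INR > 1.5"; or at 3 X ULN or more with a listed symptom or sign, or eosinophilia.
- **Preexisting elevation.** Clause 1: a further rise to 8 X ULN or more that the underlying condition does not explain. Clause 2: 3 X ULN or more, "with at least 50% increase from transaminase values collected at Day 1", plus a newly appearing listed sign. Clause 3: "Clinically significant worsening of liver function associated with further transaminase elevations in a subject with abnormal transaminase levels already meeting the above criteria". A parenthesis restates the clause 1 and clause 2 thresholds and ends by placing them at baseline.

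Three other places bear on this. Exclusion 14 (5.1.3) removes a subject who "has any of the following laboratory abnormalities at the time of screening", including ALT or AST of 4 X ULN or more and total bilirubin of 3 X ULN or more. Footnote 11 of the Trial Flow Chart (6.0) has Day 1 chemistry drawn before the first dose. Section 8.4.1 takes baseline as the last pre-dose value, typically from Visit 2, which is Day 1.

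**The concern.** Clauses 1 and 2 rest on the transaminase level, or on the level plus symptoms. Only clause 3 looks at liver function, and its precondition excludes nearly everyone the trial can enrol. The bilirubin/INR rule, which might have covered the same ground, sits in the other branch. A subject with a modestly raised ALT at entry can thus develop a combined rise in transaminase and bilirubin without meeting any objective stop.

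This matters here because liver abscess and complicated cholecystitis are eligible diagnoses, baseline ALT or AST up to just under 4 X ULN is allowed, section 4.1.2 reports transaminase rises with relebactam (including in Japanese subjects in PN012), and safety is a primary objective.

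**Working it through.** The plan gives no figure to reproduce; the check is of the rule's logic. All values are multiples of ULN, and *b* is baseline ALT. 'Preexisting elevation' is not defined in 5.8.1 and is taken as above ULN, so 1 < *b* < 4.

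**Step 1: can clause 3's precondition be met at baseline?**

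- Limb 1 needs *b* ≥ 8. Screening ALT must be below 4, so the required rise between screening and the pre-dose sample is 8 / (screening value): 8/3.99 = 2.005-fold, 8/3 = 2.67-fold, 8/2 = 4.0-fold. This is possible in principle, but it requires more than a doubling within at most 24 hours and before any study drug.
- Limb 2 needs (baseline value)/(Day 1 value) ≥ 1.5. With baseline taken as the Day 1 pre-dose sample, the ratio is *b*/*b* = 1.0. It fails for every *b*.
- Stepping *b* from 1.01 to 3.99 by 0.01 gives 299 values; none meets either limb.

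**Step 2: does a looser reading rescue the clause?** Suppose 'at baseline' modifies only the abnormal transaminase levels. Clause 3 then still needs 8 X ULN or more, or 3 X ULN or more with new signs. A subject below 8 X ULN without new signs remains outside it.

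**Step 3: the same on-treatment values from two baselines.** On treatment: ALT 5.0, bilirubin 3.0, no new listed sign, no eosinophilia.

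| Baseline | Test | Result |
|---|---|---|
| ALT 0.9 | Bilirubin rule: 5.0 ≥ 3 and 3.0 > 2 | Mandatory stop |
| ALT 2.0, bilirubin 0.8 | Clause 1: 5.0 < 8 | Not met |
| | Clause 2: 5.0/2.0 = 2.5 ≥ 1.5, but no new sign | Not met |
| | Clause 3: 2.0 < 8; ratio 1.0 < 1.5 | Not met |

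In the second subject ALT has risen 2.5-fold and bilirubin 3.0/0.8 = 3.75-fold.

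**Step 4: extent of the gap.** It covers baseline ALT above 1 and below 4, rising on treatment to at least 3 and below 8, with new bilirubin above 2 X ULN or INR above 1.5, and no new listed sign or eosinophilia. If 'preexisting' meant at least 2 or at least 3 X ULN, the affected baselines would narrow to 2 to < 4 or 3 to < 4.

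**The case against.** The strongest reply is that clause 3, on its own terms, was only ever meant for subjects already past the other thresholds at entry. Exclusion 14 makes that group nearly empty, so the clause is redundant text, and the harm comes from a different choice: no bilirubin stop in this branch. That is partly right. The exposure comes from the empty clause and the missing bilirubin stop together, and restoring clause 3 alone would give a judgement trigger rather than an objective one.

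Judgement is also already provided for. Treatment must stop if "A physician investigator feels it is in best interest of the subject to discontinue for any reason", and 5.8.1 separately allows the investigator or Sponsor to stop treatment for safety. Section 7.2.3.2 adds reporting within 24 hours: item 2 (ALT or AST at least 3 with bilirubin at least 2 X ULN) if ALP is below 2 X ULN, and item 3 (confirmed ALT or AST of 5 X ULN or more) whatever the ALP. The example subject would meet item 3 once the value was confirmed, subject to the note that, for preexisting elevations, counts only rises not anticipated from an underlying condition. These safeguards are real, but none is an objective requirement to stop. Subjects with normal baselines have the same discretion and still get an objective bilirubin rule.

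A separate branch is sound in itself. A subject with ALT 3.5, bilirubin 2.5 and ALP 2.5 X ULN is eligible and would exceed the other branch's trigger before dosing. That argues for a rule relative to baseline, not for having no rule.

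On practical weight, the only subject reported with the combined ALT/AST and bilirubin event in the Phase II 250 mg arms was in PN004. The investigator judged it unrelated, and it normalized on continued therapy; PN003 had none. This limits the urgency and shows that stopping has a price.

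**Conclusion.** Clause 3 is wrong as written: it reaches practically none of the subjects the trial can enrol, and nothing else in 5.8.1 supplies an objective stop for the combined rise set out above.

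A reader might infer more than the documents support:

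- *That these subjects have no liver stop.* Clauses 1 and 2 still work for them.
- *That every unstopped rise to between 3 and 8 X ULN is a defect.* With normal bilirubin, normal INR and no new sign or eosinophilia, the other branch would not stop those subjects either.
- *That clause 3 is strictly impossible.* A sharp rise before the first dose could meet its first limb.
- *That harm will be common.* The share of subjects with raised baseline values is not given, so no frequency can be claimed.

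The conclusion assumes that preexisting means above ULN and that the baseline definition in 8.4.1, written for safety endpoints, also applies here. The liver guidance in the Investigator Trial File Binder is not among the documents and may help sites. The protocol describes it as guidance on assessment and follow-up.

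**What to change.** Delete the condition that the criteria be met already at baseline, and replace clause 3 with wording such as:

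> In a subject with ALT or AST above ULN at Day 1: a rise in ALT or AST to 3 X ULN or more that is at least 50% above the Day 1 value, together with total bilirubin above 2 X ULN that is also at least 50% above its Day 1 value; or any other clinically significant deterioration in liver function that accompanies a further transaminase rise.

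The first part is objective. ALT must reach max(3, 1.5*b*): 3.0 for *b* = 2.0, 4.5 for 3.0, 5.25 for 3.5, 5.85 for 3.9. Bilirubin must exceed 2 and reach 1.5 times baseline: above 2.0 from 0.8, and at least 3.75 from 2.5.

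- ALT 2.0 to 5.0 with bilirubin 0.8 to 3.0: stop.
- ALT 3.5 to 3.6 with bilirubin 2.5 to 2.6 (a 4% rise): no stop.
- ALT 3.9 to 5.8 (a 49% rise): left to clinical judgement under the second part.

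The transaminase 50% rule is borrowed from clause 2; the bilirubin 50% condition is new to the protocol. No INR cut-off is set because INR is not in Table 15; a locally measured INR would count under the second part.

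Cost: one amended clause and a notice to sites, with no new test. Central results may arrive too late for patient management (7.1.3.1), so sites would act on local values. There may be a few more discontinuations, including subjects whose values would have normalized. Stopping is final ("Once a subject is discontinued, he/she shall not be allowed to restart treatment"), and under 8.5.2 a subject stopped before 96 hours of therapy may be excluded from the primary ME population.
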